3.1 Type/Design of Study

This is a retrospective, longitudinal, observational, study.

3.2 Study Treatments

This is a natural history study. There are no treatments being investigated in this trial.

3.3 Study Population

The study population shall consist of up to 250 Stargardt disease patients, with a minimum of 150 patients, recruited at up to 14 clinical centers across the US and Europe. Participants must be at least six years old at study enrollment. There are no limitations regarding race, ethnicity, or sex.

The participants must present with atrophic lesions secondary to STGD with a minimum diameter of 300 microns and the area of all lesions together must add to less than or equal to 12 mm² and must represent no more than 5 disc areas in a least one eye at the most recent visit (which can coincide with the screening visit of the PROGSTAR 02 study). Participants must have been genotyped to participate in the study and have at least 2 confirmed pathogenic mutations in the *ABCA4* gene. If only one *ABCA4* allele contains a pathogenic mutation, then for inclusion in this study the patient must show a typical phenotype, i.e. at least one eye must have flecks at the level of the retinal pigment epithelium typical for STGD.

3.3.1 Recruitment Methods

The investigators at each of the centers will review their own clinical patient databases and contact their patients.

3.3.2 Recruitment Process

The investigators at each of the clinical centers will identify potential study patients from their own patient populations. Potential study participants who demonstrate an interest in participating in the study will receive an explanation of the terms, and requirements of the study, in language they can understand, from an investigator in the research team. They will also receive a written copy of the Informed Consent Form to read and share with family or friends prior to their screening visit. Subsequently, an investigator or a qualified designee will answer questions and request the patient's permission to participate in the study. Participants will sign a study-specific patient informed consent form approved by the local Institutional Review Board.

For participants younger than 18 years of age, parental/LAR consent and patient assent will both be obtained prior to participation in this study.

3.3.3. Volunteer Compensation

This observational study collects existing information on the natural course of STGD and all examinations were part of the standard clinical care. Compensation will not be provided to the study participants.

3.3.4. Recruitment Materials

No centrally prepared recruitment or advertising materials are planned for this study. Recruitment materials such as telephone scripts or written letters may be prepared by individual sites.

3.4 Eligibility Criteria

3.4.1 Informed Consent/Assent

When individuals are identified in-person as potential study participants, the investigator will provide information about the study, and confirm contact. The investigator or other designated study staff will obtain and document informed consent from appropriate, interested patients.

Potential study participants who demonstrate an interest in participating in the study will receive an explanation of the terms and requirements of the study from the research team in a language they can understand. They will receive a copy of the Informed Consent Form to read and share with family or friends. An investigator or designated site study staff member will answer any questions or concerns that the potential participants may raise and request the patient's permission to participate in the study. Each site will provide adequate time for the patient to make a decision whether to participate in the study. When the potential participant is a minor (less than 18 years of age), parental consent/LAR and minor participant assent will be obtained following the same procedures outlined in the previous paragraph. The minor participant will be provided with an age appropriate assent form and given a chance to freely choose whether to participate in the study.

Study candidates who cannot give their own consent to participate will only be enrolled into the study after consent is obtained from the individual's Legally Authorized Representative (LAR). Children shall receive an additional assent form written in age appropriate language for them to read, and will only be enrolled into the study following consent by their individual's Legally Authorized Representative (LAR). Site investigators will consult with their local institutional review boards for guidance regarding who may serve as an LAR.

For study candidates who are illiterate or unable to understand the written consent form, the consent form will be read and explained to them in the presence of a witness. The candidate must sign or mark the form in an individually unique manner, such as with a thumbprint, to indicate their agreement to participate. A witness may also sign the form to

attest that the content of the written consent form was conveyed accurately to the study candidate.

If a study candidate is not fluent in the primary language of the host country of the study site, all documentation including the consent form and any site information sheets approved by the local IRB shall be translated into their native language by a certified translator and the translation approved by the local IRB and HRPO. Plans shall also be made and approved to ensure a qualified translator is available during the consent process, baseline and all follow-up visits to address any concerns or ensure they provide continuing consent to study participation.

When consent is obtained in a language other than English, the foreign language version of the consent form will be a certified accurate translation of the English version of the consent form.

Written informed consent shall be obtained from all participants or their LAR before any data will be collected for study use. However, investigators may discuss in general the availability of the study and the general entry criteria with a potential participant candidate without obtaining consent.

The investigator has both an ethical and legal responsibility to ensure that each participant study candidate being considered for inclusion in this study is given a full explanation of the protocol. This shall be documented on the written informed consent form approved by the same Institutional Review Board (IRB) responsible for approving this protocol.

Once the appropriate essential information has been provided to the participant and fully explained by the investigator, or a qualified designee, and the participant understands the implications of participating, the IRB-approved written informed consent/assent form(s) will be signed and dated by the participant and the person obtaining consent (investigator or designee), and by any other parties required by the site's local IRB. The participant shall be given a copy of the signed informed consent form. The original signed informed consent form shall be kept on file by the investigator; the time length will be determined by the local IRB. All of the above mentioned activities shall be completed prior to the participant's participation in the trial.

3.4.2 Disclosure of DOD Sponsorship and Access to Research Records

The informed consent form shall include a statement that discloses that the DOD is supporting the research and that representatives of the USAMRMC have the authority to review research records of any study participant. Study candidates have a right to decline participation in research based on the source of the funding.

3.4.3 Inclusion Criteria

Study participants are required to meet the following inclusion criteria:

Table 3.4.3-1 Inclusion Criteria	
1.	Provide a signed informed consent/assent form and authorization allowing the disclosure and use of protected health information.
2.	The study eye must have at least one well-demarcated area of atrophy as imaged by fundus autofluorescence with a minimum diameter of 300 microns and the area of all lesions together must add to less than or equal to 12 mm ² (equivalent to no more than 5 disc areas in a least one eye) at the most recent visit.
3.	Two (2) or more pathogenic mutations confirmed present, in the ABCA4 gene. If only one ABCA4 allele contains pathogenic mutation(s), the patient shall have a typical Stargardt phenotype, namely at least one eye must have flecks at the level of the retinal pigment epithelium typical for STGD.
4.	Sufficient quality of imaging and psychophysical procedures in the opinion of the investigator.
5.	Patients have been followed for at least two (2) visits over a period of at least 24 months, up to 60 months, and had at least two examinations (same at all visits out of: Fundus Autofluorescence obtained with a Heidelberg Engineering instrument (e.g. HRA2, Spectralis); sd-OCT obtained with the Heidelberg Spectralis; Microperimetry obtained with the Nidek MP-1).
6.	Be at least six years old at the most recent visit (“visit -1”).
7.	Both eyes can be included if inclusion criteria are fulfilled for both eyes.

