Participant Population:	Up to a total of 250 (minimum of 150) patients, including males and females age 6 years and older affected by STGD that have an atrophic lesion in at least one eye with a minimum diameter of at least 300 microns, and a sum of all lesions areas less than or equal to 12 mm ² (five disc areas) at the most recent visit. Participants must have been previously genotyped to participate in the study and have at least 2 confirmed pathogenic mutations in the ABCA4 gene. If only one ABCA4 allele contains a pathogenic mutation, then the patient needs to show a typical phenotype, i.e. at least one eye must have flecks at the level of the retinal pigment epithelium typical for STGD.	
Test Product, Dose, Mode of Administration:	N/A	
Outcome variables:	
 • Growth or development of atrophic lesions as measured by FAF imaging over a period of at least 24 months, and up to 60 months. • Rate of retinal thinning and photoreceptor loss as measured by sd-OCT over a period of at least 24 months, and up to 60 months. • Loss of retinal sensitivity as measured by microperimetry over a period of at least 24 months, and up to 60 months. • Change of best-corrected visual acuity over a period of at least 24 months, and up to 60 months. 	
Study Duration:	Total duration of study including patient enrollment and data analysis: 12 months.	

Table of Contents

Protocol Synopsis	5
Table of Contents	7
1 Introduction	14
1.1 Background.....	15
1.2 Treatment Strategies	18
1.3 Known and Potential Risks	19
1.3.1 Foreseeable Risks	19
1.3.2 Risk Management and Emergency Response.....	19
1.3.2.1 Minimization of Risk.....	19
1.3.2.2 Response to Risk	20
1.3.2.3 Research Injury Compensation.....	20
1.3.2.4 Precautions and Preventive Measures	20
1.3.3 Known and Potential Benefits.....	20
2 Study Rationale and Objectives	20
2.1 Study Rationale	20
2.2 Study Objectives.....	21
3 Study Design.....	21
3.1 Type/Design of Study.....	23
3.2 Study Treatments.....	24
3.3 Study Population	24
3.3.1 Recruitment Methods	24
3.3.2 Recruitment Process	24
3.3.3. Volunteer Compensation.....	25
3.3.4. Recruitment Materials	25
3.4 Eligibility Criteria.....	25
3.4.1 Informed Consent/Assent	25
3.4.2 Disclosure of DOD Sponsorship and Access to Research Records	26
3.4.3 Inclusion Criteria	26
3.4.4 Exclusion Criteria.....	28
3.5 Primary and Secondary Outcome Variables.....	29
3.6 Measures to Minimize/Avoid Bias	29
3.6.1 Blinding.....	29
3.6.2 Study Data	30

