3.7.2. Endpoints

3.7.2.1. Primary Statistical Endpoint

The primary endpoint is the rate of the growth or the development of atrophic lesions as measured by FAF imaging calculated over a period of at least 24 months, up to 60 months.

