7.2. Statistical Analyses

Estimating **the yearly growth in the area of the atrophic lesion** as measured by fundus auto-fluorescence:

First exploratory analysis looking at the overall distribution of the outcome at all visits will be carried out, outliers and inconsistent measures will be identified and reviewed. By design, the interval between visits will be variable. For each individual, a slope will be estimated using the available data points by fitting a regression line to the data points. For example, if the i^{th} subject contributes with 3 visits the times $t_{i0}, t_{i,-1}, t_{i,-2}$ with outcome observations $y_{i0}, y_{i,-1}, y_{i,-2}$ will be used to estimate the slope b_i , which will be obtained from the regression $y_{ik}=a+b_i t_{ik}$. ($k=0,-1,-2$). Once the data from each individual has been used to estimate the slope (b), the second stage of the analysis will be to explore which exposures/risk factors determine the heterogeneity of the slopes. Using the slope as the outcome, multivariate regression models will be constructed to identify factors correlating

with progression. Specifically, the correlation to progression of age, severity at first visit, and use of vitamin A supplementation will be examined.

A similar approach to will be used to examine progression over time for the secondary outcomes: retinal thinning, loss of photoreceptors, loss of retinal sensitivity, and changes of BCVA.

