Statistical Analysis Plan

ProgSTAR Study

FFBCRI-PROGSTAR-01	The Natural History of the Progression of Atrophy Secondary to Stargardt Disease: A Retrospective Longitudinal Observational Study
FFBCRI-PROGSTAR-02	The Natural History of the Progression of Atrophy Secondary to Stargardt Disease: A Prospective Longitudinal Observational Study
FFBCRI-PROGSTAR-02a	SMART Study: Scotopic Microperimetric Assessment of Rod Function in Stargardt Disease
Version	1.0
Date:	19 May 2018
Prepared for:	Foundation Fighting Blindness
Prepared by:	[name] and [name] Wilmer Eye Institute Johns Hopkins University

ProgStar Statistical Analysis Plan

Participant demographic and clinical characteristics at baseline (or the first ProgStar visit from the medical record review for the retrospective cohort) are first summarized. The progression rates of outcome measures from each testing modality (visual acuity from ETDRS test; mean sensitivity from microperimetry; decreased autofluorescence [AF] from fundus AF imaging; and retinal thickness and intact area from OCT) are estimated and reported separately. For each outcome, cross-sectional analysis using linear models with generalized estimating equations is first conducted for baseline data to understand factors associated with significantly different levels of baseline measurements. Longitudinal analysis is then conducted for each outcome to estimate its rate of progression and the associated risk factors. The data are longitudinally plotted over time to visualize the change during study period. A linear mixed-effects model (LMM) with a random intercept and a random coefficient for time is used to estimate the overall rate of change per year in the prospective and retrospective cohort, respectively. LMMs are also used to estimate the rates of change in subgroups stratified by the baseline level of the outcome. To further identify baseline variables associated with the rate of change, LMMs are used by including each baseline variable and its interaction with time. The univariate association of each variable with the change rate of the outcome variable is first estimated. Adjusted associations are also estimated using multivariable LMMs including variables either significantly associated with the change of outcome at p<0.1 or significantly associated with baseline outcome at p<0.1.

Additional statistical methods as appropriate for model construction are described in individual publications.

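### PROGSTAR-01 applies its 12 mm² lesion ceiling at the visit that ends the outcome window, so its planned analyses by first-visit lesion size can show falsely slower growth in larger lesions, or hide faster growth

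*Protocol*

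**What the plan says.** **When the ceiling applies.** PROGSTAR-01 Section 3.4.3, criterion 2, requires a total lesion area of at most 12 mm² in the study eye, "equivalent to no more than 5 disc areas in a least one eye) at the most recent visit". The PROGSTAR-01 synopsis ("five disc areas) at the most recent visit") and Section 3.3 ("no more than 5 disc areas in a least one eye at the most recent visit") agree. Criterion 6 labels this visit −1, the last of the series. Section 3.3 adds a detail about it: "which can coincide with the screening visit of the PROGSTAR 02 study". One measurement can therefore end the PROGSTAR-01 window and start PROGSTAR-02.

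**What is estimated.** Section 3.7.2.1 reads: "The primary endpoint is the rate of the growth or the development of atrophic lesions as measured by FAF imaging", over 24 to 60 months.

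**How it is analysed.** Section 7.2 works in two stages. First: "For each individual, a slope will be estimated using the available data points by fitting a regression line to the data points". The slopes then become the outcome: "Specifically, the correlation to progression of age, severity at first visit, and use of vitamin A supplementation will be examined". The SAP replaces this with a linear mixed model that "is used to estimate the overall rate of change per year in the prospective and retrospective cohort, respectively". It defines baseline in the retrospective cohort as the first visit from the record review, estimates rates in strata of the baseline level, and carries variables into the multivariable model at p<0.1.

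**What is not addressed.** Section 7.5 expects no missing main outcome data. Neither document mentions selection by the ceiling. The SAP leaves further methods to individual publications but promises no correction.

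**The concern.** Eligibility is decided on the last value of the outcome, while the analysis sorts eyes by the first value. For a given follow-up time, the larger the first lesion, the less it can have grown and still be under 12 mm² at the end. Fast growers are therefore missing, and mostly from the large-lesion strata. An analyst who follows the plan exactly could report that larger lesions grow more slowly when the ceiling alone produced the pattern, or could miss a true acceleration with size.

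Section 2.2 says the data are meant to help evaluate efficacy measures for planned trials. Those trials will follow patients forward from baseline, so a false size gradient could misdirect stratification or the choice of patients.

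**Working it through.** **The plan's own figure.** No stated figure bears on this selection. The nearest is the sample size in PROGSTAR-01 Section 7.1. For a difference of 0.2, SD 0.9, two-sided α 0.05 and 80% power, (1.960 + 0.842)² × 0.9²/0.2² = 159. Dividing by the Wilcoxon efficiency 3/π gives 167, against the stated 170. It reproduces and is not in dispute.

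**Inputs from the documents.** Ceiling 12 mm²; window T = 2 to 5 years; cited growth mean 0.94, SD 0.87 mm²/year (Section 7.1). Reader error also comes from Section 7.1: the confidence interval for the mean difference has half-width 0.10 in 34 eyes, so the SD of a difference is 0.10/2.03 × √34 = 0.29, or 0.29/√2 ≈ 0.20 mm² per reading.

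**Step 1: the cap.** Inclusion requires first area + rate × T ≤ 12, so rate ≤ (12 − first area)/T.

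| First area (mm²) | Cap, T = 2 | Cap, T = 5 |
|---|---|---|
| 1 | 5.5 | 2.2 |
| 7 | 2.5 | 1.0 |
| 10 | 1.0 | 0.4 |
| 11 | 0.5 | 0.2 |

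From 7 mm² upward, part or all of the range of caps lies close to or below the cited mean of 0.94.

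**Step 2: what the cap does to a mean of 0.94.** Take gamma growth with shape k = (0.94/0.87)² = 1.167 and scale 0.87²/0.94 = 0.805. The share kept at cap c is F_k(c), and the mean among kept eyes is 0.94 × F_{k+1}(c)/F_k(c).
- First area 1 mm²: 99.8% kept with mean 0.93 (T = 2); 91% kept with mean 0.74 (T = 5).
- First area 10 mm²: 65% kept with mean 0.44 (T = 2); 31% kept with mean 0.20 (T = 5).

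**Step 3: by stratum.** Simulation with T uniform on 2–5 years, first areas uniform on 0.07–12 mm², no measurement error, and true mean 0.94 everywhere:

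| First area (mm²) | 0–2 | 2–4 | 4–6 | 6–8 | 8–10 | 10–12 |
|---|---|---|---|---|---|---|
| Observed mean | 0.85 | 0.79 | 0.72 | 0.60 | 0.42 | 0.21 |
| Kept | 97% | 94% | 88% | 79% | 59% | 24% |

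Truncated exponential first areas (scale 4 or 2) give nearly the same stratum means.

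**Step 4: masking.** The coefficient of rate on first area, in mm²/year per mm², under the three first-area distributions (uniform; exponential 4; exponential 2):
- true 0 is observed as −0.057, −0.046, −0.036;
- true +0.05 is observed as −0.031, −0.024, −0.015, so the sign reverses;
- true +0.10 is observed as −0.001, 0.000, +0.007.

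**Step 5: timing is the cause.** With n = 170 and no true association, a significant negative association appears in 99%, 63% and 18% of samples under the three distributions. With the ceiling moved to the first visit it appears in 2.2–2.4%, against a nominal 2.5%.

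**Step 6: a smoother illustration.** Lognormal first areas with median 1–5 mm² (log-SD 0.8, or 0.5 in one variant), gamma growth, error SD 0.20, strata formed on observed first area, every eye with a first-visit lesion, and equal true growth in all strata:

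| Growth mean/SD | Shortfall, >5 against ≤2 mm² | Chance of a false negative association, p<0.05, n = 250 eyes |
|---|---|---|
| 0.4/0.4 to 0.5/0.5 | about 12–24% | about 7–70% |
| 0.94/0.87 | about 25–33% | about 14–97% |

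Without the ceiling the last column is 2–4% (medians 2–5). Measurement error in the first area adds a little to the gradient. For medians 2–5, stratifying on true instead of observed area gives 13–21% instead of 15–24% in the first row, and 28–32% instead of 29–33% in the second.

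**The case against.** **The protocol defines its population at the most recent visit.** Section 3.3 does so explicitly, and describing the past course of eyes that are eligible now is a legitimate aim. This stands. A reader might infer that the overall PROGSTAR-01 rate is biased low. That follows only against a different target, eyes eligible at the start of the window, which the protocol does not set. Figure 6 also admits eyes whose lesion appeared later (Scenario 2) or that give no growth rate (Scenario 3), and the simulations leave them out.

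**The sizes are not bounds.** This also stands. The documents give no first-visit area distribution, and the chance of a false association falls steeply if first lesions are small or little spread. The growth settings 0.4/0.4 and 0.5/0.5 are also assumptions, since Section 7.1 plans SDs of 0.9 to 1.1. The direction does not depend on any of this.

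**A gap between the cohorts.** A reader might infer that PROGSTAR-01 must report slower growth than PROGSTAR-02. With constant growth, eyes kept in PROGSTAR-01 keep the same rate in PROGSTAR-02. Any gap would come from eyes that enter PROGSTAR-02 without an earlier lesion, so none is claimed here.

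**Onset.** The words on growth or development might suggest that the study promises an onset rate it cannot deliver. No onset hazard is promised. Figure 6 assigns development to secondary variables, Section 7.1 names yearly growth in area as primary, and Section 7.2 estimates only that. What remains is loose wording.

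**A modelled correction is fragile.** When the overall mean is adjusted for truncation with a gamma slope model, a true 0.94 is recovered as 0.96 if slopes are gamma, but as 0.85–0.86 if they are lognormal. A normal-slope version gives 0.81–0.83. That argues for a sensitivity analysis, not a replacement.

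**Conclusion.** The concern holds for the size–growth analyses. The ceiling at visit −1 truncates growth more tightly as first area and follow-up time rise, and both the second-stage regression in Section 7.2 and the SAP's baseline-level strata condition on that first area. Neither document corrects for it. A falsely negative relation, or a hidden positive one, can follow from executing the plan as written.

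The direction is certain if atrophy does not shrink. The size is illustrative and rests on the assumed first-area distribution, gamma growth, uniform follow-up and an error SD of 0.20. That SD comes from readings of geographic atrophy in age-related macular degeneration, not from repeat imaging in Stargardt disease. The documents do not support the stronger conclusions that the overall rate is invalid or that the sample size is wrong. The development wording is a minor, separate inconsistency.

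**What to change.** Keep eligibility as it is.

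**(a) Add to the SAP:**

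> PROGSTAR-01 growth rates, overall and by first-visit area, are conditional on a total area of at most 12 mm² at the most recent visit. A lower rate in larger first-visit lesions is not interpreted as biological from PROGSTAR-01 alone. The relation of baseline area to growth is read primarily from PROGSTAR-02, where the ceiling applies at baseline. As a sensitivity analysis, the PROGSTAR-01 size–growth coefficient and stratum rates are re-estimated with a likelihood that conditions on the last area being at most 12 mm², given first lesion-positive area and follow-up time. It includes measurement error, uses at least two slope distributions, and clusters standard errors by person. Results are reported beside the naive ones.

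**(b) Minor wording.** Reconcile growth or development in the PROGSTAR-01 synopsis and Sections 2.2, 3, 3.5 and 3.7.2.1 with Figure 6 and Section 7.1. Growth rate is primary. Development is described only among eyes that were lesion-free at an earlier visit, and no onset rate is estimated, because every included eye has a lesion at visit −1.

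**Cost.** Some programming and a text change; no new patients, charts or visits. Adjusted standard errors in the large-lesion strata are much wider: about 0.2 against 0.05 in one check at 0.94/0.87 (gamma model, 5–12 mm² stratum, 450 independent eyes, 50 replicates). That check was a favourable case, with the fit started at the true values. The adjusted result also depends on the assumed slope distribution, so it supplements the naive rate.
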